Five hundred thirty adult male and female English- or Spanish-speaking current smokers who are patients at one of seven federally qualified health centers (FQHC) within the Near North Health Services Corporation (NNHSC) community clinic system will be enrolled in this clinical trial.

Inclusion Criteria

Eligible participants will be males and females who are:

1. 18 years of age or older;
2. A patient at one of the seven participating NNHSC community clinics;
3. Listed as “current someday smoker” or “current everyday smoker” in their NNHSC EHR; confirms current someday or everyday smoking status at phone screen
4. Have had ≥ 1 visit to their NNHSC clinic within the past 12 months

Exclusion Criteria

Participants who self-report any of the following will not be eligible to participate in the study:

1. Documented within their NNHSC EHR as preferring a language other than English or Spanish for healthcare;
2. No telephone number or address listed in the EHR;
3. Does not have a cell phone with texting capabilities;
4. Lives with another NNHSC patient who is already enrolled in the present study.

[figure not shown]
Vulnerable Populations

Children under 18 years of age, fetuses, neonates, or prisoners will not be included in this study. Pregnant women will not be actively recruited, but will be eligible for the study if they meet all other inclusion and exclusion criteria detailed above.

STUDY DESIGN

This is a 2-group randomized controlled trial to evaluate the effectiveness of the population health management intervention for low-income smokers that aims to promote Quitline treatment, engagement, utilization, and smoking cessation (Figure 1).

Figure 1. Study Design

Length of Study Participation

PROTOCOL SHORT TITLE: Choose to Change – Reducing Tobacco Disparities

Participants will be involved in study-related activities for approximately 7½ months (32 weeks) from initial enrollment in the observational study and baseline assessment (week -4) through follow-up (week 28). Participants will complete four phone-based assessments during this time (Baseline/Week -4; Week 6; Week 14, Week 28) and those who report abstinence from cigarettes at the Week 28 phone interview will be asked to come in for an in-person clinic visit within 2 weeks of their Week 28 phone session in order to bioverify smoking status.

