Treatment engagement will be measured at 6, 14, and 28 (as applicable) weeks after letter mailing, and operationalized as the proportion of participants who accept the proactive Quitline call and accept treatment as defined by completing the counseling session. Participants who return a Quitline call and accept treatment also will be counted as having engaged in treatment. Further, we will assess: 1) the proportion of smokers who request cessation versus reduction counseling; and 2) the proportion of smokers who engage in treatment and who request NRT and (or) schedule a follow-up (proactive or reactive) counseling call.

Treatment utilization will be measured at 6, 14, and 28 (as applicable) weeks and will be defined as the proportion of participants who complete ≥ 1 additional counseling calls and receive and use NRT. The frequency and duration of sessions will also be measured.

Smoking cessation at 6 and 14 weeks will be defined as self-reported abstinence (not even a puff of a cigarette) for ≥ 7 days. At 28 weeks, breath CO will be used to verify abstinence for participants in the original study timeline. For participants in the alternative shorter study timeline, breath CO will be measured at 14 weeks to verify abstinence. Participants will be classified as abstinent if they report not smoking (not even a puff of a cigarette) for ≥ 7 days and have a CO ≤ 8 parts per million (ppm). Participants will be assumed to be smoking if they report smoking, cannot be reached to provide data, fail to provide a breath sample, or provide a breath sample that is >8 ppm.¹⁰⁵ Participants who report abstinence at 28 weeks (original timeline) or 14 weeks (alternative shorter timeline) will be invited for an in-person visit for breath carbon monoxide (CO) measurement to bio-verify abstinence status.

Moderators, Mediators, and Covariates

Hypothesized moderators of Choose to Change effects will be measured at baseline and include readiness to quit smoking,^{96,97} recent smoking reduction,⁵¹ cigarettes per day, time since last clinic visit during which smoking was addressed, initial choice of cessation versus reduction, race/ethnicity, perceived stress, , and discrimination. Hypothesized mediators of intervention effects on treatment engagement, utilization, and cessation will be measured at each survey time point and will include perceived autonomy support, autonomous motivation, confidence in ability to quit, and attitude towards NRT.

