All outcomes of interest for **Primary Aims 1-3** are binary (treatment engagement, treatment utilization, smoking cessation) and can be analyzed using logistic regression methods. Analyses will be conducted first using an ITT principle (missing=treatment failures). We will also conduct an adherence sample analysis that includes only participants reached at the 28-week follow-up ($\geq 75\%$ of the sample based on our experience). This approach addresses the question of effectiveness more directly, but it is subject to more bias if attrition is large or differential by treatment condition. Therefore, we will complement it by analysis of non-response patterns using sociodemographic (age, gender, race, ethnicity, marital status, household income, education), and healthcare (time since last clinic visit, type of health insurance) characteristics. These can be used to create propensity scores that allow for inverse-probability-weighting (IPW) of observed outcomes^{116,117} to achieve balance across potential confounders of the treatment-to-outcome relationship. Ideally, the distribution of propensity scores will show large overlap across study conditions. If not, that will be taken as evidence that completers are not comparable on measured confounders across conditions, and that one should refrain from

PROTOCOL SHORT TITLE: Choose to Change – Reducing Tobacco Disparities

further comparisons. PROC GENMOD of SAS/STAT 9.2¹¹⁸ can handle subject-level probability weights. Similar findings across all three approaches would increase confidence in the results overall. Both raw and adjusted rates will be presented for each outcome by study condition. For the cessation outcome, we will also explore the impact of smoking history (e.g., past year quit attempts, past referral for Quitline treatment), race, and gender on non-response. We will also use propensity score modeling to examine the relationship between treatment utilization at 14 weeks and abstinence at 28 weeks. Since available data indicate little effect of NRT type on outcome, we will model NRT dose/duration, while controlling for patterns of utilization.

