The setting for this study will be Winfield Moody Health Center, which is the flagship clinic and administrative location for NNHSC, and the NU Preventive Medicine Research Clinic ([name]). All aspects of the study, i.e., query list identification, outreach recruitment calls, all telephone surveys, intervention letter creation, sending of intervention text messages, mailing of recruitment and retention materials, in-person clinic sessions, will take place at either Winfield Moody or the NU Preventive Medicine Research Clinic. Additionally, for participants who report abstinence at their week 28 phone session, they will be offered the option to conduct the in-person clinic visit at either their home NNHSC clinic location or the NU Preventive Medicine Research Clinic.

Prior Approvals

The NNHSC Research Committee has reviewed and approved the study protocol.

CONSENT PROCESS

Baseline and follow-up surveys will be completed by telephone; therefore, verbal informed consent will be obtained from patients prior to being enrolled. To obtain verbal informed consent, the RA will read the IRB-approved informed consent document to the candidate that includes all components of a standard informed consent form, including study description and procedures, risks and benefits of participation, alternatives to participation, financial information, protection measures taken to ensure participant confidentiality, research subject rights, and who to contact with any questions or concerns about the study. Enrolled smokers will be given the option to receive the informed consent form, via traditional mail or email, that was used to document their verbal consent and signed by the RA who obtained the consent.

During each telephone surveys, participants will be encouraged not to answer any question that makes them feel uncomfortable. It will be explained during consenting and before administration of all surveys that they may stop the survey at any time and that doing so would not negatively affect their healthcare.

Participants enrolled in the alternative/shorter study timeline will be read an edited consent that accurately explains the shorter timeline and corresponding compensation. All other aspects of the consenting process will be the same as the participants completing the original study timeline.

Incomplete Disclosure

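### For CO-verified cessation (Aim 3), all three planned analyses code a self-reported quitter without a breath sample as a smoker, so their agreement cannot reveal bias from CO-visit attendance

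*Combined protocol and SAP*

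**What the plan says.** Cessation in Aim 3 is bio-verified seven-day abstinence at week 28. Participants in the shorter timeline are verified at week 14 instead.

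Verification follows the telephone survey. Under Length of Study Participation, "those who report abstinence from cigarettes at the Week 28 phone interview will be asked to come in for an in-person clinic visit". The shorter timeline has the same sequence at week 14.

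Treatment Outcomes (Measures) fixes the coding: "Participants will be assumed to be smoking if they report smoking, cannot be reached to provide data, fail to provide a breath sample", or give a sample above 8 ppm. Not being reached and not giving a sample are listed as separate routes to the same value.

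The Data Analysis section sets out three approaches:

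- **Intention to treat:** "Analyses will be conducted first using an ITT principle (missing=treatment failures".
- **Reached sample:** "We will also conduct an adherence sample analysis that includes only participants reached at the 28-week follow-up", expected to be at least 75% "of the sample based on our experience".
- **Weighted:** propensity scores built from sociodemographic and healthcare characteristics are used to weight the observed outcomes.

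It then says: "Similar findings across all three approaches would increase confidence in the results overall". For cessation it also plans to explore whether smoking history, race and gender are related to non-response. A self-report-only cessation outcome is defined for weeks 6 and 14, but none is defined for week 28.

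**The concern.** The cessation outcome can be lost at two stages. A participant may not be reached by telephone. Or a participant may be reached, report abstinence, and not attend the CO visit. The reached-sample and weighted analyses vary the handling of the first stage only. At the second stage the value is already fixed as smoking before any of the three analyses begins.

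A reader who sees three similar estimates would take them as evidence that missing data did not drive the result. For the second stage the similarity is built in and carries no information. The expected numbers are small: 2% and 7% of 265 are about 5 and 19 verified quitters. A handful of missed visits in one arm can therefore move the estimate noticeably.

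**Working it through.** **The plan's own figure.** Aim 3 power with 2% v 7%, 265 per arm and two-sided alpha 0.05, pooled normal approximation:

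- Mean rate = (0.02 + 0.07)/2 = 0.045.
- Null SE = √(2 × 0.045 × 0.955/265) = 0.01801.
- Alternative SE = √((0.02 × 0.98 + 0.07 × 0.93)/265) = 0.01788.
- z = (0.05 − 1.96 × 0.01801)/0.01788 = 0.82, so power = 79.5%.

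The stated 80% reproduces. The point below concerns outcome coding, not this calculation.

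**Following one participant through the plan.** Take someone who reports abstinence at the week 28 call and does not attend the visit.

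| Analysis | Included? | Outcome used |
|---|---|---|
| Intention to treat | yes | smoking |
| Reached sample | yes, because reached | smoking |
| Weighted | yes, because reached | smoking, multiplied by a weight |

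No row restricts on, weights for or recodes CO-visit attendance. The Data Analysis section names only week 28. If its approaches are carried over to the shorter timeline, the same holds at week 14.

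**Illustration.** From the documents: 75% reached, the lower bound in Data Analysis. Assumed: true abstinence q = 7% in both arms (no effect), honest self-report, every attender passes the CO test, and attendance a differs by arm. The attendance values are assumptions because the documents give none.

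- Intention-to-treat rate = 0.75 × q × a.
- Reached-sample rate = q × a.
- Weighting for being reached: here reach is the same for everyone, so the weights are constant and the result equals the reached sample.
- Odds ratio = Choose to Change odds divided by Usual Care odds.

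At 40% (Usual Care) v 60% (Choose to Change):

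- Intention to treat: 0.75 × 0.07 × 0.4 = 2.10% v 0.75 × 0.07 × 0.6 = 3.15%. OR = (0.0315/0.9685)/(0.0210/0.9790) = 1.52.
- Reached: 2.8% v 4.2%. OR = (0.042/0.958)/(0.028/0.972) = 1.52.
- In people: 265 × 0.75 × 0.07 = 13.9 self-reported quitters per arm, of whom 5.6 v 8.3 are verified.

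| Attendance, Usual Care v Choose to Change | OR, intention to treat | OR, reached | OR, weighted | OR, self-report |
|---|---|---|---|---|
| 40% v 60% | 1.52 | 1.52 | 1.52 | 1.0 |
| 30% v 70% | 2.38 | 2.40 | 2.40 | 1.0 |
| 60% v 40% | 0.66 | 0.66 | 0.66 | 1.0 |

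The three planned estimates agree almost exactly in every row, whatever the direction of the bias.

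**The same mechanism can hide a benefit.** Suppose 4% v 14% of those randomised report abstinence. Attendance of 50% in both arms gives the planned 2% v 7%. Attendance of 60% v 40% gives 0.04 × 0.6 = 2.4% v 0.14 × 0.4 = 5.6%, for which power is 46.8%.

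**If unverified quitters were instead dropped as missing from the reached sample.** The odds in each arm become q × a/(1 − q), so the OR is the attendance ratio: 0.6/0.4 = 1.5. This is again close to the intention-to-treat 1.52. The listed weighting variables do not include self-reported abstinence, which determines who is invited.

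**The case against.** Counting unverified quitters as smokers is a conservative rule, and the point does not ask to replace it. The agreement sentence is modest and covers all three primary aims. For Aims 1 and 2 CO attendance is irrelevant. The cessation-specific look at non-response and the week 14 self-report outcome go some way, but neither changes the coding and neither is one of the three approaches.

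The strongest objection is that differential attendance is unproven. Retention mailings and the $50 visit payment are the same in both arms, and the letter and texts end within about four weeks of mailing. That stands. A difference is still possible in either direction, because only Choose to Change participants get the provider letter, the texts and automatic Quitline referral. But nothing in the documents shows that a difference exists.

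Four stronger readings are tempting and not supported:

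- *Visit loss erodes the stated 80% power.* The aims define 2% and 7% as bio-verified rates and Table 3 labels them intent-to-treat. Visit loss is already inside them, and applying it again counts it twice.
- *The 81% or 60% under Retention and Adherence indicates CO attendance.* The first is session completion in another trial and the second is expected survey participation. Data Analysis gives a third figure, at least 75% reached. None concerns CO visits.
- *Shorter-timeline participants are denied the home-clinic option*, because Setting says "for participants who report abstinence at their week 28 phone session, they will be offered the option to conduct the in-person clinic visit". The alternative-timeline text keeps all other procedures the same, and Study Sites places in-person sessions at participants' home clinics. Randomisation is the same in both timelines, so a location difference would not separate the arms.
- *Robustness may be claimed only if self-report agrees with the primary result.* Self-report may itself be inflated differently by arm, which is what CO testing is there to catch.

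**Conclusion.** The point holds for CO-verified cessation only. Agreement among the three planned analyses can inform on loss from not being reached. It gives no information on bias from CO-visit attendance that differs by arm.

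The conclusion about coding follows from the text. It rests on taking a participant who answered the telephone survey as reached, which Treatment Outcomes supports by listing not reached and no breath sample separately. It largely survives the other reading.

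The size is illustrative: with no true effect, a 20-point attendance gap gives an OR of about 1.5 or about 0.66, depending on direction. A reader might infer that the trial's cessation result will be biased. The documents do not support that, since they give no attendance rate in either arm. What is established is that the plan as written could not show such a bias if it occurred. This merits a change to the analysis plan but does not undermine the primary definition.

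**What to change.** Keep the primary rule. Add to Data Analysis, for Aim 3:

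1. A sensitivity analysis fitting the same logistic model to self-reported seven-day abstinence at the verification time point (week 28, or week 14 in the shorter timeline), regardless of CO attendance.
2. A table by arm of CO-visit attendance among self-reported abstainers, and of the CO confirmation rate among those who attend.
3. Optionally, an exploratory analysis that weights or imputes the CO result among self-reported abstainers.

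Reword the agreement sentence so that, for cessation, it refers only to loss from not being reached. State that any difference between the self-report and primary results will be read alongside attendance and confirmation by arm, and will not serve as a pass-or-fail test of robustness.

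The cost is one model, one table and a few sentences, using data the surveys and visits already collect. The downsides are that self-report can be misreported, possibly differently by arm, and that item 3 will be imprecise because there will be few self-reported quitters.

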PROTOCOL SHORT TITLE: Choose to Change – Reducing Tobacco Disparities

[figure not shown]
outcomes.⁹⁹ Text messaging improves attendance at healthcare visits,^{100,101} adherence to diabetes self-care¹⁰² and weight management regimens,¹⁰³ as well as the effectiveness of smoking cessation treatment.⁹⁹ Popularity of text messaging is high across racial/ethnic groups, socioeconomic levels, and ages.¹⁰²

Two weeks after letter mailing, participants will be contacted by a Quitline counselor and offered free person-centered behavior counseling (cessation or reduction-focused depending upon patient preference) and free NRT (patch, gum, or lozenge) if determined as safe and appropriate. Please see more detail regarding the proactive Quitline treatment below.

Usual Care Condition: Participants assigned to this clinic-based control comparison will receive NNHSC clinic-based care for smoking that follows the Ask, Advise, Refer approach.¹⁹ Following the practice adopted by NNHSC in 2011, a Usual Care participant who smokes will receive a referral for proactive Quitline treatment according to the following established clinic procedure: If the participant is seen in the clinic for a health problem or routine evaluation, a medical assistant will confirm current smoking and advise the participant to quit using clear and strong language. Current smoking and advice to quit are documented in the EHR system and the participant will be seen by the provider who addresses the purpose of the visit. If the provider also addresses the participant's smoking, establishes that the participant is motivated to set a quit date, and the participant agrees to the Quitline referral, a referral form is generated via the EHR system. Referrals are transmitted electronically via the Quitline website by the Care Coordinator. Participants who are referred will receive a call from the Quitline within 48 hours. Usual Care participants who accept Quitline treatment will receive free person-centered smoking cessation counseling and free NRT (patch, gum, or lozenge). Please note: providers may still refer patients who are not enrolled in this study to the Quitline.

In both conditions, Quitline treatment will continue as accepted or initiated by participants over 28 weeks.

Figure 3. Choose to Change Intervention Workflow

Choose to Change Intervention Clinic Workflow

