Participants in both treatment conditions will have the opportunity to receive the same proactive Quitline treatment consisting of person-centered behavior counseling and NRT. The Quitline protocol relies on treatment determined to be effective in the 2008 U.S. PHS Clinical Practice Guideline.⁵ Participants who are reached and who accept treatment will first be asked for basic sociodemographic and smoking information. After registration and brief assessment, either smoking cessation- or reduction- focused treatment will be delivered depending on patient preference. Participants who choose reduction as their initial treatment goal will be guided toward setting a quit date aided by NRT. For all participants who engage in treatment, a self-help packet (Quit-Kit) will be mailed to provide written information on the topics covered during the initial phone session. Most calls last about 30 minutes, with the behavior counseling portion lasting about 15 minutes. A free 8-week course of NRT (patch, gum, or lozenge) will be mailed in two week allotments to participants who are willing to set a quit date and interested in and eligible to use NRT (i.e., free of medical contraindication). Per Quitline policy for Chicago residents, NRT is offered at no cost for uninsured residents and reduced cost for those who have Medicaid insurance. Because free NRT increases use of quitline treatment,^{46,104} NRT will be made available at no cost to all participants to eliminate differential cost by insurance type as a potential confounder of intervention effects.

If a participant is reached by the Quitline counselor but has not received the Choose to Change letter, smoking cessation or reduction treatment will be offered and delivered according to the participant's preference. For participants not reached during the first call attempt, the Quitline counselor will make two more calls in the following two days. A voice message will only be left if the voicemail inbox belongs to the referred participant. If three calls are made without a response, the outreach process will end. The Quitline counselor will either call at times designated by the participant to be convenient or at varying times during the day. The Quitline provides services seven days per week, from 7:00 AM through 11:00 PM.

MEASURES

EHR Characterization of Population

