PROTOCOL SHORT TITLE: Choose to Change – Reducing Tobacco Disparities

enroll patients in the study or referral to the Quitline, all NNHSC providers will be able to exclude patients whom should not attempt smoking cessation; b) clear instructions for declining participation will be provided in the Choose to Change letter, i.e., the patient may call the study care coordinator and request that his/her name and contact information not be securely transmitted to the Quitline; and (c) patients will be given the opportunity at the start of the Quitline call to decline participation.

Patients who engage in Quitline treatment may experience mild discomfort when asked about smoking or concerns related to smoking cessation or gradual smoking reduction. Additionally, for participants who quit smoking or reduce, it is possible that they will experience symptoms of tobacco withdrawal. The most common symptoms of withdrawal are anxiety, irritability, difficulty concentrating, insomnia, and restlessness. The Quitline counselors are trained to help patients manage withdrawal symptoms. Patients will be reminded that these symptoms are typically time-limited and they will be taught behavioral strategies to manage symptoms. A free 8-week course of nicotine replacement therapy (NRT; patch, gum, or lozenge) will be mailed in two week allotments to patients who are free of medical contraindications and complete weekly counseling calls. For participants who can safely use nicotine replacement therapy (e.g, the patch, gum, or lozenge) and elect to do so, use of NRT will minimize the severity of withdrawal. Participation in the study does not otherwise involve any physical or emotional risk to study participants beyond that of everyday life.

Potential Benefits to Subjects

Potential benefits for patients are smoking cessation and the associated health and psychological benefits. We expect that successful smoking reduction will build self-confidence and substantially increase the likelihood of the smoker making a quit attempt and achieving successful smoking cessation by eight months. A potential benefit for NNHSC is improved preventive care and improved health for its patients. If the proposed intervention is determined to be effective, we will be able to disseminate it to Alliance's 11 safety net health centers throughout Chicago, comprising over 85 clinical sites that care for almost 500,000 patients.

Study Subject Compensation

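### As written, the supplementary NRT dose/duration model, adjusted for utilization, cannot be read as an exposure-response

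*Combined protocol and SAP*

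**What the plan says.** The Data Analysis section closes its account of Primary Aims 1-3 with two supplementary analyses. The first reads "We will also use propensity score modeling to examine the relationship between treatment utilization at 14 weeks and abstinence at 28 weeks". The second, on NRT, reads "we will model NRT dose/duration, while controlling for patterns of utilization". The NRT sentence does not name its outcome; abstinence is inferred from the sentence before it. Nor does it say whether dose means NRT mailed or NRT used, over what period dose is counted, or how smoking during treatment is handled.

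Other sections bear on it:

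- **Release of NRT.** Both descriptions give an 8-week course. Under Proactive Quitline Treatment it "will be mailed in two week allotments to participants who are willing to set a quit date and interested in and eligible to use NRT". Under Potential Study Risks it "will be mailed in two week allotments to patients who are free of medical contraindications and complete weekly counseling calls". Only the second ties mailing to calls.
- **Utilization.** Treatment Outcomes defines it as "the proportion of participants who complete ≥ 1 additional counseling calls and receive and use NRT".
- **Treatment period.** The end of the Usual Care description says "In both conditions, Quitline treatment will continue as accepted or initiated by participants over 28 weeks".
- **Outcome date.** Verified abstinence is at week 28 on the original timeline. On the other, "For participants in the alternative shorter study timeline, breath CO will be measured at 14 weeks to verify abstinence".
- **Propensity covariates.** These are introduced for the non-response analysis: sociodemographic variables "and healthcare (time since last clinic visit, type of health insurance) characteristics". For cessation, smoking history, race and gender are also to be explored in relation to non-response. None is measured during treatment.

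**The concern.** Total NRT is something a participant accumulates over up to eight weeks, and how long that lasts may depend on how the quit attempt is going. If those who return to smoking tend to leave treatment, long duration marks people who were already succeeding. A model of abstinence on duration then mixes any effect of NRT with who stayed in treatment.

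The stated adjustment does not separate the two. Utilization as defined in Treatment Outcomes contains the exposure, and under the Potential Study Risks wording the calls also control its release. At stake is an apparent dose-response for the free 8-week course that could be published from this trial although duration did nothing.

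**Working it through.** **1. The plan's own figures.** The documents give no figure for this model. The nearest are the powers for the randomized comparisons at n = 265 per arm. With z = [|p2 − p1|√n − 1.96√(2p̄q̄)] / √(p1q1 + p2q2), Aim 3 (2% v 7%) gives (0.814 − 0.575)/0.291 = 0.82, a power of 79.5% (stated 80%). The same formula gives 99.1% for Aim 1 (stated 99%) and 83.9% for Aim 2 (stated 84%). All reproduce, and none depends on the NRT model.

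**2. Can a null effect produce a gradient?** Assumptions, none from the documents: everyone receives a first allotment; relapse risk is 30% per two weeks; later abstinence is 50% without relapse and 5% with it; unrelated dropout is 15% per two weeks; NRT has no effect. Overall abstinence is 0.7⁴ × 0.50 + (1 − 0.7⁴) × 0.05 = 0.120 + 0.038 = 15.8%.

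Now let half of relapsers stop per two weeks.

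- *Four allotments.* Setting aside unrelated dropout, which cancels, the share reaching the fourth is 0.343 (no relapse yet) + 0.0375 + 0.0525 + 0.0735 (relapsed in period 1, 2 or 3 but continuing) = 0.5065. Of these, 0.343 × 0.7 = 0.240 end unrelapsed, or 47.4%. Abstinence = 0.05 + 0.45 × 0.474 = 26%.
- *One allotment.* The share stopping after the first is 0.3 × (1 − 0.5 × 0.85) + 0.7 × 0.15 = 0.1725 + 0.105 = 0.2775. Of these, 0.105 × 0.343 = 0.036 end unrelapsed, or 13%. Abstinence = 0.05 + 0.45 × 0.13 = 11%.

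So an inert treatment shows 11% abstinence after one allotment and 26% after four.

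**3. Does the adjustment remove it?** Same assumptions, odds ratio (OR) per extra allotment in a simulated population of 400,000:

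| Relapsers stopping per two weeks | Unadjusted | Adjusted for calls |
|---|---|---|
| 0% | 1.00 | 1.00 |
| 10% | 1.11 | 1.11 |
| 25% | 1.25 | 1.25 |
| 50% | 1.48 | 1.49 |
| 80% | 1.72 | 1.66 |

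In these runs calls and allotments correlate at 0.91 to 0.93, so the adjustment costs precision and leaves the bias. Adding relapse during treatment to the model returns an OR of about 1.0.

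**4. Direction.** With equal stopping in both groups the OR is 1.00. If abstainers stop sooner (50% v 30%, or 40% v 15% per two weeks) it is 0.87 or 0.83.

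**5. Size in this trial.** Expected engaged participants: 0.24 × 265 + 0.10 × 265 = 63.6 + 26.5 ≈ 90. Assumptions: 60% start NRT; 10% or 20% quit long-term (9 or 18 people); the others relapse at a mean of 4 weeks; unrelated dropout is 15% per week; no NRT effect. A logistic model of quitting on number of allotments, adjusted for any further call, gives:

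| Relapsers stopping NRT at relapse | False-positive rate (nominal 5%) |
|---|---|
| None | about 2% to 5% |
| Half | about 5% to 9% |
| All | about 17% to 24% |

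The median false OR per allotment is about 1.08 if half stop and 1.3 if all do. Between 6% and about 25% of fits give no usable estimate.

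**6. Start date.** Choose to Change outreach comes about two weeks after the letter, whereas Usual Care referral follows a clinic visit at any time. Someone starting at week 10 can have at most 14 − 10 = 4 weeks of NRT by week 14, but can finish all eight by week 18, before a week-28 outcome. The cap therefore matters for the shorter timeline or a week-14 cut-off. It is not in the simulations.

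**7. Is exposure at the first call cleaner?** Only with readiness in the model. Assume half are ready to quit, with long-term quitting 30% v 10% and NRT start 90% v 30%. First allotment yes/no then gives about 24% to 26% false positives without readiness and about 2% with it.

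**The case against.** The strongest reply is that this is one supplementary, non-randomized sentence that makes no causal claim. That stands, and it limits the weight of the point.

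Several stronger readings are tempting, and the documents do not support them:

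- *Relapse ends NRT supply.* No section says so. The call condition is in Potential Study Risks but not in Proactive Quitline Treatment, and the Quitline also counsels people who are still smoking and have chosen reduction. Stopping at relapse is a plausible inference only.
- *A useless dose would look effective.* That holds only if relapsers stop sooner than abstainers; step 4 shows the reverse case.
- *The false-positive rate could be about 70%.* Simulations reach 69% to 72% if every engaged participant starts NRT and every relapser stops. The plan restricts NRT to willing, interested and eligible participants, so this is an extreme. First allotment yes/no could not be estimated there at all, because it would not vary.
- *Adjusting for utilization creates the bias.* Conditioning on something that determines exposure mainly costs precision. The fault is that it does not remove the bias. The Aim 2 hypothesis states utilization as calls alone, which would avoid the overlap in definition, but step 3 shows that adjusting for calls still leaves the bias.
- *No such model can be built.* A landmark with on-treatment smoking handled as a time-varying confounder, or a purely descriptive label, would be defensible. The plan specifies neither.

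None of these replies supplies what the sentence lacks: an outcome, a dose metric, an exposure window and a way of handling smoking during treatment.

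**Conclusion.** The point holds in limited form. Following the sentence as written gives a coefficient that cannot separate an NRT effect from persistence in treatment, and the one stated adjustment does not help. Neither the size nor the direction of the bias can be fixed from the documents. The false-positive rates in step 5 range from close to nominal to several times nominal, and they rest entirely on assumed relapse, stopping and NRT-start rates. An uncertain direction does not rescue the estimate; it leaves it uninterpretable either way. The randomized comparisons of Aims 1 to 3 and their power are untouched. The change is worth making before analysis because it is cheap and governs what may be claimed about NRT.

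**What to change.** Replace the NRT sentence in Data Analysis with the following commitments:

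1. Report weeks of NRT shipped or used descriptively by arm, saying which, and state that no dose or duration effect on abstinence will be inferred.
2. If an NRT association is modeled, name the outcome and fix the exposure at the first completed counseling call (first allotment yes/no), or at a stated landmark before the outcome.
3. In that model, adjust for baseline readiness to quit, already collected as a randomization stratifier, and for weeks from randomization to that call, in addition to the listed propensity covariates. Do not adjust for utilization as defined in Treatment Outcomes.
4. Reconcile Proactive Quitline Treatment and Potential Study Risks on whether NRT mailing depends on completing weekly calls.
5. Confirm that the Quitline can supply NRT shipment dates. The documents say that treatment outcomes are transmitted but do not mention shipment dates.

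The cost is analysis-plan wording and one data query. The trial gives up a dose-response claim, and any first-call association remains observational.
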